COVER PAGE FOR PROTOCOL AND STATISTICAL ANALYSIS PLAN

Official Study Title:

Can Exenatide Prevent the Increase in EGP in Response to Dapagliflozin-induced Increase in Glucosuria

NCT number: NCT03331289

IRB Approval Date: 03/21/2019

Unique Protocol ID: HSC20170582H

Protocol Template Form

Item 1 UTHSCSA Tracking Number	HSC20170582H
Item 2 Abstract / Project Summary	
Provide a succinct and accurate description of the proposed research. State the purpose/aims. Describe concisely the research design and methods for achieving the stated goals. This section should be understandable to all members of the IRB, scientific and non-scientific.
 
DO NOT EXCEED THE SPACE PROVIDED.

Purpose/Objectives: To examine whether coadministration of the GLP-1 receptor agonist exenatide (a potent inhibitor of glucagon and stimulator of insulin secretion) with an SGLT2 inhibitor dapagliflozin can prevent/ameliorate the compensatory rise in Endogenous Glucose Production (EGP) and produce an additive, even synergistic decrease in the plasma glucose concentration
 
Research Design/Plan: After screening, each subject will receive 1 measurements of EGP with prime-continuous Infusion of 3-3H-glucose. After completing the EGP measurement each subject will receive a Double Tracer OGTT.
 
Methods: Visit 1: Screening. Medical history will be obtained, physical exam performed, and pregnancy test performed. Visit 2: Endogenous Glucose Production Measurement: The rate of EGP will be measured with 3-3H-glucose. Visit 3: Double Tracer OGTT
 
Clinical Relevance: The primary end point is the change in EGP. The difference in rate of EGP during the last hour of the study (from 240-300 minutes) between drug-treatment and placebo treatment studies represents the effect of drug treatment on EGP, which will be compared among the 3 drug. treatments (exenatide; dapagliflozin; exenatide plus dapagliflozin) with ANOVA
	

Item 3 Background	

Describe past experimental and/or clinical findings leading to the formulation of your study.
 
For research involving unapproved drugs, describe animal and human studies.
 
For research that involves approved drugs or devices, describe the FDA approved uses of this drug/device in relation to your protocol.
	
Insert background: Glucosuria produced by inhibition of the renal sodium-glucose transporter-2 (SGLT2) lowers the fasting plasma glucose (FPG) concentration but causes a “paradoxical” increase in endogenous glucose production (EGP). Although the increase in EGP can be viewed as a compensatory mechanism that opposes urinary glucose loss and prevents the development of hypoglycemia in NGT individuals, in T2DM individuals it occurs while the plasma glucose concentration is still in the hyperglycemic range. Moreover, it offsets by ~50% the urinary glucose loss produced by SGLT2 inhibitors and attenuates their glucose lowering ability. The increase in EGP following SGLT2 inhibition is associated with an increase in plasma glucagon concentration and decrease in plasma insulin concentration. Because renal glucose production is stated to be unresponsive to an increase in the plasma glucagon concentration, it is likely that the liver contributes, at least in part, to the increase in EGP [which is triggered by glucosuria]. However, an increase in glucose production by the kidney cannot be excluded. We hypothesize that there is a previously unrecognized, [completely novel] “reno-hepatic” interaction that participates in the regulation of plasma glucose concentration. This “reno-hepatic axis” is [activated by glucosuria] and stimulates hepatic, as well as renal, glucose production. The aim of the present study is to: (i) determine the source of increase in EGP, liver versus kidney [or both]; and (ii) examine the signal activated by glucosuria that is responsible for the increase in EGP.

Item 4 Purpose and rationale Insert purpose, objectives and research questions/hypotheses here. If you cut and paste from another document, make sure the excerpted material answers the question	Insert purpose: Understanding the factors that regulate EGP is key to understanding normal glucose homeostasis and development of hyperglycemia in T2DM. We and others have shown that glucosuria produced by SGLT2 inhibition (SGLT2i) stimulates EGP, indicating the presence of an interaction between the kidney and liver, i.e. "a renohepatic axis" that coordinates the regulation of EGP and plasma glucose conc . The present study will provide evidence for the existence of this previously unrecognized reno-hepatic axis and define the mechanisms responsible for the interaction between the kidney and liver. In addition to providing novel insights about the regulation of glucose homeostasis, the present study has important clinical implications. Although SGLT2i are effective in producing glucosuria, they cause only a modest decrease in HbA1c (0.6-0.8%). On one hand, the presence of a "reno-hepatic axis" that leads to a compensatory increase in EGP in response to glucosuria maintains the FPG in NGT individuals and prevents hypoglycemia. On the other hand, the increase in EGP in T2DM individuals is "paradoxical" in that it occurs while plasma glucose conc is in the hyperglycemic range and offsets by ~50% urinary glucose loss (10) (see results below) produced by SGLT2 inhibitors and attenuates their glucose lowering effect. Thus, determining the mechanisms that mediate the rise in EGP in response to glucosuria will allow the development of strategies that prevent the rise in EGP and increase the efficacy of SGLT2.
---	---

Item 5 Study Population(s) Being Recruited In your recruitment plan, how many different populations of prospective subjects do you plan to target? Provide number: 1 e.g., a population can be individuals with type 2 diabetes controlled with diet and/or a population of healthy controls. Or a population can be individuals attending an education program, etc. List each different population on a separate row and provide a short descriptive label : (e.g., normal-healthy, diabetics, parents, children, etc.) To add rows use copy & paste	Identify the criteria for inclusion :	Identify the criteria for exclusion :
T2DM according to ADA criteria	subjects must be in good general health as determined by physical exam, medical history, blood chemistries, CBC, TSH, EKG and urinalysis 18-70 years old 21-45 kg/m Male and Female $\geq 7.0\%$ and \leq up to 10.5% Drug naïve and/or on a stable dose (more than 3 months) of metformin and/or sulfonylurea	Subjects who are Type 1 Diabetes, have proliferative diabetic retinopathy, plasma creatinine >1.4 females or >1.5 males will be excluded. Subjects taking drugs known to affect glucose metabolism (other than metformin and sulfonylurea)

Item 6

Research Plan / Description of the Research Methods *a. Provide a comprehensive narrative describing the research methods. Provide the plan for data analysis (include as applicable the sample size calculation).*

Step-by-Step Methods:

After screening, eligible subjects will receive a measurement of endogenous glucose production (EGP) with a prime-continuous infusion of 3-³H-glucose. The EGP measurement will be performed in the morning after a 10-12 hour overnight fast and will last 8.5 hours (from 6 AM to 2:30 PM). After a 3.5-hour tracer equilibration period, subjects (20 per group) will receive one of the following medications: (i) placebo; (ii) exenatide 5 ug subcutaneously; (iii) dapagliflozin (10 mg); and (iv) dapagliflozin 10 mg plus exenatide 5 ug (see flowsheet for EGP). Following the test medication at 9:30 AM, blood samples will be drawn every 15 minutes for an additional 5 hours and plasma glucose, insulin, C-peptide, glucagon, and glucose specific activity will be measured.

Visit 1: Screening. Medical history will be obtained and physical exam will be performed. Blood will be drawn for FPG, routine blood chemistries, CBC, lipid profile, HbA1c, and thyroid function. Urinalysis, EKG, albumin/creatinine ratio and pregnancy test will be performed.

Visit 2: Endogenous Glucose Production Measurement: The rate of endogenous glucose production will be measured with 3-³H-glucose infusion. [3-³H]-glucose infusion will be started at 6 AM and continued until 2:30 PM (5 hours after drug administration). At 6 AM a catheter will be placed into an antecubital vein and a prime (40 uCi x FPG/100)-continuous (0.4 uCi) infusion of [3-³H]- glucose will be started and continued until 2:30 PM. (5 hours after drug administration). Participant's hand will be placed in a box heated to 50-60°C (122-140°F). Baseline blood samples will be obtained at -210, -60, -50, -45, -40, -35, -30, -20, -10, and 0. After 3.5 hours of tracer equilibration blood samples will be obtained every 10-20 minutes from 9:30 AM to 2:30 PM. Plasma glucose, insulin, C-peptide, glucagon, and [3-³H]-glucose specific activity will be measured. Urine will be collected from 6 to 9:30 AM and from 9:30 AM to 2:30 PM. Urinary volume and glucose concentration will be measured and urinary glucose excretion rate calculated. The study will end at 2:30 PM. The total amount of blood taken during this time is 164 ml or 12 tablespoons.

Visit 3: Double Tracer Oral Glucose Tolerance Test (DT-OGTT): Within one to two weeks after the measurement of EGP, all subjects will have a 5-hour DT-OGTT with measurement of plasma glucose, insulin (I), C-peptide (CP), and glucagon concentrations at -180, -6, -5, -45, -40, -35, -30, -20, -10, 0 and every 15-30 minutes thereafter to obtain a measure of overall glucose tolerance, insulin secretion ($\frac{\text{ICPO-120}}{\text{IGO-120}}$), insulin sensitivity (Matsuda index [MI]), beta cell function, ($\frac{\text{ICPO-120}}{\text{IGO-120}} \times \text{MI}$), and suppression of plasma glucagon concentration (64). At 7 AM a catheter will be placed into an antecubital vein and a prime (25 uCi x FPG/100)-continuous (0.25 uCi) infusion of [3-³H]-glucose will be started and continued until 3 PM. Urinary volume and glucose concentration will be measured and urinary glucose excretion rate calculated. The total amount of blood taken during the OGTT is 226 ml about 15 tablespoons. HbA1c will be measured twice, once on the day of the DT-OGTT and once on the day of the EGP measurement.

Note: *The repeated double tracer listed in the grant application will not be performed as part of this protocol. The grant will be amended to remove at continuing review of the grant application.*

Data Analysis Plan: The primary end point is the change in EGP. The difference in rate of EGP during the last hour of the study (from 240-300 minutes) between drug-treatment and placebo treatment studies represents the effect of drug treatment on EGP, which will be compared among the 3 drug treatments (exenatide; dapagliflozin; exenatide plus dapagliflozin) with ANOVA. Post hoc testing will be performed with Bonferroni correction for multiple comparisons. The following primary comparison will be performed: (i) change in EGP above baseline following dapagliflozin alone versus dapagliflozin/exenatide.

Item 7 Risks Section:

Complete the following table to describe the risks of all **research procedures** listed in Step 2, Institutional Form (items 28-34). *Do not list risks of Routine care procedures here.*

N/A, Risks are described in the informed consent document – do not complete this table.

Research procedures	Risks
example: 
• History and physical• Questionnaire• Laboratory tests Add or delete rows as needed	List the reasonably expected risks under the following categories as appropriate:
Chart Review	
Serious and likely;
 
○ Insert risk here or enter "none" 
Serious and less likely;
 
○ Insert risk here or enter "none" 
Serious and rare;
 
○ Insert risk here or enter "none" 
Not serious and likely;
 
○ Insert risk here or enter "none" 
Not serious and less likely
 
○ Breach of confidentiality

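### Background metformin and sulfonylurea use has no place in the EGP analysis; a prespecified ANCOVA would use it almost for free, for a gain of 0 to 6 power points

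*Combined protocol and SAP*

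**What the plan says.** Item 5 (inclusion criteria) accepts people with type 2 diabetes who are drug-naive or "on a stable dose (more than 3 months) of metformin and/or sulfonylurea". That allows four background states: none, metformin, sulfonylurea, or both. The exclusion criteria bar "Subjects taking drugs known to affect glucose metabolism (other than metformin and sulfonylurea"), so the protocol itself treats these two drugs as exceptions within a class that it otherwise keeps out.

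The comparison is between subjects. In the Item 2 abstract, "each subject will receive 1 measurements of EGP with prime-continuous Infusion of 3-3H-glucose", and in Item 6 "subjects (20 per group) will receive one of the following medications". Neither item describes how subjects are allocated or whether therapy is balanced across groups.

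The Data Analysis Plan in Item 6 contains two descriptions of the outcome. It says "The primary end point is the change in EGP", and its one named primary comparison is "change in EGP above baseline following dapagliflozin alone versus dapagliflozin/exenatide". Between these it defines the drug effect as "The difference in rate of EGP during the last hour of the study (from 240-300 minutes) between drug-treatment and placebo treatment studies", to be "compared among the 3 drug treatments (exenatide; dapagliflozin; exenatide plus dapagliflozin) with ANOVA". It names no covariate or stratification factor.

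**The concern.** A factor that the protocol regards as relevant to glucose metabolism varies between subjects, and the analysis ignores it. If background therapy is related to the outcome, two things follow. The variation it causes stays in the error term and lowers power. And with 20 per arm, the estimated contrast shifts with whatever therapy mix the arms happen to have. Prespecification also matters: if an imbalance shows up and no adjustment was planned, the decision whether to adjust will be made with the data in view.

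**Working it through.** **1. What each outcome definition leaves in.** Let therapy shift a subject's EGP level by *b*, before and after dosing alike, and shift the post-dose change by a further *c*. Let *g* be the difference between the dapagliflozin and dapagliflozin/exenatide arms in the proportion treated.

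- Change above baseline: expected contrast = true effect + *c·g*. The level effect *b* cancels.
- Last-hour EGP, drug minus placebo: in parallel groups the same placebo mean is subtracted from both drug arms, so it drops out of their contrast. Expected contrast = true effect + (*b + c*)·*g*. The level effect does not cancel.

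Item 6 schedules pre-dose samples from -210 to 0 minutes, so a baseline exists for every subject. The documents give no value for *b* or *c*.

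**2. Reference power.** The plan gives no sample-size calculation, alpha, SD or target difference, so 20 per group cannot be reproduced. Assuming two-sided alpha 0.05 for the single primary comparison, the difference detectable with 80% power is (1.960 + 0.842) × √(2/20) = 0.886 SD by the normal formula. It is 0.897 SD with the t distribution on 80 − 4 = 76 degrees of freedom. I use 0.9 SD.

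**3. Precision.** If therapy explains a share R² of the outcome variance (assumed), adjustment multiplies the residual SD by √(1 − R²), so the standardised difference becomes 0.9/√(1 − R²).

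| R² (assumed) | Standardised difference | Power | Subjects per arm for the same precision, 20(1 − R²) |
|---|---|---|---|
| 0 | 0.900 | 80% | 20 |
| 0.05 | 0.923 | 82% | 19 |
| 0.10 | 0.949 | 84% | 18 |
| 0.15 | 0.976 | 86% | 17 |

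Using 73 instead of 76 degrees of freedom changes these powers by less than 0.1 point. To calibrate R²: with half the subjects treated, a therapy shift of *s* within-therapy SDs gives R² = 0.25*s*²/(1 + 0.25*s*²). That is 0.06 at *s* = 0.5 and 0.14 at *s* = 0.8, so the top of the range needs a large therapy effect on the outcome.

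**4. Chance imbalance.** Assume simple randomisation and a treated proportion *p*. The numbers treated in the two primary arms are independent Binomial(20, *p*). The exact probability that they differ by at least 4 is 0.268 at *p* = 0.5 and 0.226 at *p* = 0.3 or 0.7. For a gap of at least 5 it is 0.154 and 0.119.

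**5. What a gap does to the estimate.** A gap of 4 of 20 (*g* = 0.20) shifts the contrast by 0.20 × 0.5 = 0.10 SD if therapy shifts the outcome by 0.5 SD, and by 0.20 × 0.8 = 0.16 SD at 0.8 SD. The standard error of the contrast is √(2/20) = 0.316 SD, so these shifts are about one third and one half of a standard error.

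**6. Type I error.** In simulation (20 per arm, half treated, therapy shift 0.4 or 0.8 SD, no drug difference), the unadjusted t-test rejects about 5.0% of the time overall.

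**The case against.** The strongest reply is that the endpoint and the only named primary comparison are changes from each subject's own baseline, and therapy must have been stable for over three months. A constant effect on level is therefore already removed. Harm then requires therapy to predict the change after a single test dose, and nothing in the documents shows that it does. The exclusion wording is an eligibility label and says nothing about acute response. R² may be zero, and then both costs vanish. One could equally ask for adjustment by HbA1c, BMI or sex.

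Most of this stands, and it is why the precision range starts at no gain. Two things survive it. The last-hour sentence in the same paragraph does not remove the level effect, and the plan does not say which definition governs. And therapy is the one subject characteristic that the protocol itself carves out of an exclusion aimed at glucose metabolism, which is a better reason to choose it than habit.

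A reader might infer that the plan carries a raised false-positive rate. The documents and the arithmetic do not support that. Under randomisation the overall rate stays at 5%. Treating a 5-of-20 gap as a pure shift of 0.1 to 0.2 SD suggests 6 to 10%, but this ignores that the unadjusted error variance already contains the therapy spread. Simulated with that included, the rate given such a gap is about 5.5% to 7.5% for therapy effects of 0.4 to 0.8 SD, and it falls below 5% when the arms are balanced.

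A reader might also take the 23 to 27% as the probability of a biased result. It is the probability of an unequal mix, which matters only if therapy is related to the outcome.

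**Conclusion.** The point holds as a modest, inexpensive improvement to the analysis. The population is mixed on a factor that the protocol marks as relevant, and the stated ANOVA makes no use of it. The loss is 0 to 6 power points around a reference of 80%, if therapy explains 0 to 15% of outcome variance, together with an estimate that is sensitive to the mix obtained. A gap of at least 4 of 20 between the primary arms has probability 23 to 27% if 30 to 70% of subjects are treated.

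The treated proportion, the R² range, the alpha and the 0.9 SD reference are all assumptions, because the documents give none of them. The effect is near zero if the change definition governs and therapy acts on level only. It is larger if the last-hour definition governs and therapy affects the level. The imbalance figures also presuppose randomisation, which the text does not describe; without it, a difference in mix need not be due to chance.

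**What to change.** Replace the ANOVA with a prespecified ANCOVA of EGP at 240-300 minutes on arm (four levels, placebo included), baseline EGP and background therapy (drug-naive / metformin only / any sulfonylurea). Name dapagliflozin versus dapagliflozin/exenatide as the primary contrast. With baseline EGP in the model, the arm contrasts are the same whether the outcome is written as last-hour EGP or as change from baseline, so the conflict between the two definitions no longer affects this comparison.

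If allocation is randomised and enrolment is still open, stratifying by drug-naive versus treated is optional. It would not balance sulfonylurea use among treated subjects; the covariate deals with that.

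The cost is a few lines of analysis text and three residual degrees of freedom (one for baseline EGP, two for therapy), from 76 to 73. No new measurement is needed: the baseline samples are already scheduled, and therapy must be known to apply the eligibility criteria. If therapy does not predict the EGP change, its inclusion will add little.

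### The plan calls drug minus placebo the drug effect but tests only among the three drugs, so the 20 placebo subjects enter no stated test

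*Combined protocol and SAP*

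**What the plan says.** The aim in Item 2 (Purpose/Objectives) is to examine whether exenatide given with dapagliflozin "can prevent/ameliorate the compensatory rise in Endogenous Glucose Production (EGP". Under Research Design/Plan, "each subject will receive 1 measurements of EGP with prime-continuous Infusion of 3-3H-glucose". Item 6 (Step-by-Step Methods) assigns each subject one of four treatments, 20 per group: placebo, exenatide, dapagliflozin, or both drugs.

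The Data Analysis Plan in Item 6 has four relevant statements:

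- The endpoint: "The primary end point is the change in EGP".
- The effect: the difference in EGP rate over 240-300 min "between drug-treatment and placebo treatment studies represents the effect of drug treatment on EGP, which will be compared among the 3 drug treatments", by ANOVA. Item 2 (Clinical Relevance) repeats this definition.
- Multiplicity: "Post hoc testing will be performed with Bonferroni correction for multiple comparisons".
- The one primary comparison: "change in EGP above baseline following dapagliflozin alone versus dapagliflozin/exenatide".

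For the baseline, Visit 2 states: "Baseline blood samples will be obtained at -210, -60, -50, -45, -40, -35, -30, -20, -10, and 0". It does not say which of these samples form the baseline EGP.

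**The concern.** The effect sentence reads as though each subject had both a drug study and a placebo study. In this parallel design nobody does. Placebo can then enter the stated analysis only as a group mean subtracted from everyone, and that changes no comparison among the drugs. The ANOVA is limited to the three drug treatments and the primary comparison to two of them, so nothing in the plan tests a drug against placebo.

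This matters because the question has two parts. The first is whether dapagliflozin raised EGP in these subjects. The second is whether adding exenatide abolished that rise or only reduced it. Dapagliflozin versus the combination shows that the two arms differ, but not where either stands relative to no active drug. Change from baseline is no substitute. The fast continues through 5 hours of post-dose sampling, and only the placebo arm separates a drug effect from drift over time.

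A smaller concern is the primary variable. The 240-300 min definition has no baseline term, and the change above baseline has no window. The plan also does not say whether the primary comparison falls under the Bonferroni correction.

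**Working it through.** **Inputs.** From the documents: four groups, 20 per group, one EGP study per subject, a last-hour window of 240-300 min. The supplied text gives no alpha, power, effect size or SD behind the 20 per group, so that figure cannot be reproduced. Assumed: normal data, equal variances, randomised allocation, two-sided 5%, SD of last-hour EGP equal to 1, and a correlation rho of 0.3 to 0.7 between baseline and last-hour EGP.

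**1. Does subtracting the placebo mean bring placebo into the ANOVA?** If every drug-group value y becomes y − c, each group mean and the grand mean also fall by c. Both sums of squares, and so F, are unchanged. In a simulated data set F was 11.287 and the dapagliflozin versus combination t was 2.047, with and without the subtraction. F was also the same with an arbitrary placebo group (mean 9, SD 5).

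**2. What does the omnibus test lose by leaving placebo out?** The noncentrality is λ = 20 × Σ(mᵢ − m̄)², with 2 and 57 degrees of freedom for three groups and 3 and 76 for four. Means are in SD, in the order placebo, exenatide, dapagliflozin, combination.

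| Assumed means | 3-group power | 4-group power |
|---|---|---|
| (0, −0.5, 0.5, 0) | 79% | 74% |
| (0, 0, 0.8, 0) | 72% | 72% |
| (0, −0.5, 1, 0) | 99% | 99% |
| (0, 0, 0.8, 0.4) | 59% | 67% |
| (0, 0.2, 0.8, 0.6) | 37% | 63% |
| (0, 1, 1, 1) | 5% | 90% |

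For the fifth row, the three-group λ is 20 × (0.111 + 0.071 + 0.004) = 3.7 and the four-group λ is 20 × (0.16 + 0.04 + 0.16 + 0.04) = 8.0. In the last row the three-group λ is 0, so the test rejects only at its 5% error rate. The four-group λ is 20 × 0.75 = 15.

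**3. What does the choice of primary variable do to precision?** The outcome SD is 1 for the last-hour value, √(2(1 − rho)) for change from baseline, and √(1 − rho²) with baseline as covariate. Power is from the noncentral t with noncentrality 0.8 / (SD × √(2/20)), using the error variance pooled over four arms (76 degrees of freedom, 75 with the covariate). For a true difference of 0.8 SD:

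| rho | Last-hour value | Change | Covariate |
|---|---|---|---|
| 0.3 | 70% | 56% | 74% |
| 0.5 | 70% | 70% | 82% |
| 0.7 | 70% | 90% | 94% |

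If the primary comparison were Bonferroni-corrected over an assumed family of three, the 70% would fall to 54%.

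**4. Does a covariate model settle the value-or-change question?** Write Y for last-hour EGP and B for baseline EGP. If Y = treatment + βB + error, then Y − B = treatment + (β − 1)B + error. The treatment contrasts and their standard errors are the same, so either reading gives one result.

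**The case against.** The strongest reply is that the plan is less open than it looks. Read in sequence, the Data Analysis Plan names a change in EGP, gives the last hour as its window, and then speaks of change above baseline. The natural reading is last-hour change from baseline. Likewise, Bonferroni is attached to post hoc testing and the primary comparison is named separately, so the natural reading leaves it uncorrected. Both points stand. A reader might infer that the plan contains two rival endpoints, but the text supports only that the natural reading is not written down and that the baseline samples to be averaged are not named. The fall from 70% to 54% rests on the less natural reading.

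It can also be said that the plan does not ignore placebo, since it describes drug minus placebo as the drug effect. That is right. What is missing is a test or interval for it. Nor does one study per subject prevent such a test, since parallel groups allow it routinely. Placebo is absent chiefly because the ANOVA is restricted to the three drugs.

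Finally, the omnibus test can lose nothing by leaving placebo out, as the first three rows of the first table show. That holds for those patterns and fails for others, so no general statement about lost power is justified in either direction.

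**Conclusion.** The point holds and should be fixed. Following the plan as written, the 20 placebo subjects enter no test. Whether dapagliflozin raised EGP against concurrent placebo, and how far the combination brought it back, would go untested. This follows from the text and needs no assumed figure.

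A reader might go further and infer that the primary comparison is invalid. The documents do not support that: dapagliflozin versus dapagliflozin/exenatide is a valid between-group comparison under either definition, and with groups balanced at baseline both target the same difference. No documented figure is wrong.

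The undefined variable is secondary and affects precision. At 0.8 SD, unadjusted change has 56% to 90% power, against 74% to 94% with baseline adjustment, over rho 0.3 to 0.7. All power figures rest on the assumed effects, SD and correlation. They also assume randomised allocation, which the supplied text does not state.

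**What to change.** In Items 2 and 6, replace the effect sentence with:

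> Mean EGP over 240-300 min will be analysed in one linear model for all four arms, with treatment as a 4-level factor and baseline EGP (mean of the pre-drug samples from −60 to 0 min) as covariate. The single primary contrast is dapagliflozin versus dapagliflozin/exenatide, at two-sided 5%. The three drug-versus-placebo contrasts and the two other drug-versus-drug contrasts are secondary, Bonferroni-corrected over five. Every contrast is reported with its estimate and 95% confidence interval. Whether the combination returns EGP to the placebo level is judged from the interval for combination minus placebo, not from a non-significant test.

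The last sentence is needed because a difference test cannot show return to placebo level. If the combination stayed 0.5 SD above placebo, the test at 0.05/5 = 0.01 would detect it only 15% of the time without the covariate and 17% to 34% with it (rho 0.3 to 0.7).

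Declare these as new decisions:

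- the covariate;
- the −60 to 0 min baseline (the −210 min sample is at tracer start);
- the move from three groups to four, with contrasts replacing the omnibus ANOVA;
- the five-contrast family;
- testing the primary contrast outside that family;
- the confidence intervals.

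**Cost.** No new data, visits or subjects, but the analysis section of an approved protocol has to be revised. At 0.01 each, power for a 1 SD drug-versus-placebo effect is about 70%, rather than 88% uncorrected, before covariate adjustment. With the covariate it is 75%, 84% and 96% at rho 0.3, 0.5 and 0.7.

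### The primary EGP outcome is described in two ways that are not equivalent, and pre-dose EGP, sampled in every subject, is not used as a covariate

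*Combined protocol and SAP*

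**What the plan says.** Three statements in the Data Analysis Plan (Item 6) bear on the primary outcome:

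- The opening gives neither formula nor window: "The primary end point is the change in EGP".
- The drug effect is then "The difference in rate of EGP during the last hour of the study (from 240-300 minutes) between drug-treatment and placebo treatment studies", to be "compared among the 3 drug treatments (exenatide; dapagliflozin; exenatide plus dapagliflozin) with ANOVA". This has a time window and a placebo reference, but no baseline.
- The primary comparison is "change in EGP above baseline following dapagliflozin alone versus dapagliflozin/exenatide". This has a baseline reference, but no placebo and no window.

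The abstract in Item 2 repeats the first two statements and omits the third.

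On design, Item 2 says "each subject will receive 1 measurements of EGP", and the Step-by-Step Methods in Item 6 say "subjects (20 per group) will receive one of the following medications". The groups are therefore parallel, and no subject has a placebo session of their own. For Visit 2, Item 6 says "Baseline blood samples will be obtained at -210, -60, -50, -45, -40, -35, -30, -20, -10, and 0". That is ten pre-dose time points, nine of them from -60 to 0 minutes, with tracer specific activity measured. No covariate is named anywhere.

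**The concern.** No sentence joins the baseline, the time window and the contrast. An analyst could compare dapagliflozin with the combination on raw last-hour EGP or on change from baseline, and could defend either from the text. In one data set the two give different estimates, standard errors and possibly conclusions. The baseline window is not fixed either: the samples labelled as baseline include -210 minutes, when the tracer infusion starts.

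The sentences can be merged into change from baseline to 240-300 minutes. Baseline would then enter by subtraction only, which fixes its slope at 1 instead of estimating it. That generally gives away precision in a trial with 20 subjects per group. The supplied text does not mention random allocation. Without it, the last-hour, change-score and baseline-adjusted analyses can estimate different contrasts, which is a further reason to name one beforehand.

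**Working it through.** **Inputs from the documents.** Four groups of 20, one EGP session per subject, nine samples from -60 to 0 minutes, last hour 240-300 minutes. The documents give no SD, correlation, effect size or alpha, so no figure of the plan's own can be reproduced.

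**Assumptions.** Random allocation; two-sided 0.05; correlation *r* between baseline and last-hour EGP of 0.3 to 0.9; equal baseline and last-hour SDs unless stated; error pooled over four arms (76 df, or 75 with the covariate). Effects are in last-hour SDs.

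**Step 1: the two readings.** Let L and B be a group's mean last-hour and baseline EGP, with subscripts D (dapagliflozin), C (combination) and P (placebo).

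- Last-hour reading: (L_D − L_P) − (L_C − L_P) = L_D − L_C. The placebo mean cancels.
- Change reading, with 240-300 minutes as the end window: (L_D − B_D) − (L_C − B_C) = (L_D − L_C) − (B_D − B_C).

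They differ by B_D − B_C, whose SD is sqrt(2/20) = 0.316 baseline SD. Simulation of four-arm trials gave 0.315-0.318.

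**Step 2: relative variance of the contrast** (last-hour = 1). Change score: 2(1 − r). ANCOVA: 1 − r². The number per arm that a change score needs to match ANCOVA at 20 is 20 × 2(1 − r)/(1 − r²).

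| r | Change | ANCOVA | ANCOVA/change | Change-score n per arm to match |
|---|---|---|---|---|
| 0.3 | 1.40 | 0.91 | 0.65 | 30.8 |
| 0.5 | 1.00 | 0.75 | 0.75 | 26.7 |
| 0.7 | 0.60 | 0.51 | 0.85 | 23.5 |
| 0.8 | 0.40 | 0.36 | 0.90 | 22.2 |
| 0.9 | 0.20 | 0.19 | 0.95 | 21.1 |

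The two readings are equally precise only at r = 0.5. Estimating the slope inflates the ANCOVA variance by about 1/74 = 1.4% on average, which is not included in the table.

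**Step 3: unequal SDs.** If baseline SD is *k* times last-hour SD, the change-score variance is 1 + k² − 2rk. In the same order of r, ANCOVA/change is 0.850, 0.949, 1.000, 0.973, 0.826 for k = 0.7, and 0.476, 0.540, 0.586, 0.590, 0.543 for k = 1.3.

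**Step 4: power** (noncentral t, 20 per arm, equal SDs), shown as last-hour / change / ANCOVA.

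| r | 0.5 SD | 0.7 SD | 0.9 SD |
|---|---|---|---|
| 0.3 | 35 / 26 / 37% | 59 / 46 / 63% | 80 / 66 / 84% |
| 0.5 | 35 / 35 / 44% | 59 / 59 / 71% | 80 / 80 / 90% |
| 0.7 | 35 / 52 / 59% | 59 / 81 / 86% | 80 / 95 / 98% |
| 0.8 | 35 / 69 / 74% | 59 / 93 / 95% | 80 / 99 / >99% |
| 0.9 | 35 / 94 / 95% | 59 / >99 / >99% | 80 / >99 / >99% |

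Simulation with 40,000 four-arm trials per cell gave ANCOVA power at 0.7 SD of 0.624, 0.705, 0.857, 0.950 and 0.998. The slope cost is worth at most about 0.6 points.

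**Step 5: disagreement if both readings stay open.** In the simulation, for r = 0.3 to 0.8, the last-hour and change-score tests disagreed on significance in 27-49% of trials at 0.5 SD, 32-39% at 0.7 SD and 20-27% at 0.9 SD.

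**The case against.** The best reply is that the paragraph has one natural reading. Its first and last sentences both speak of change, and the middle one supplies the window, so the outcome is change from baseline to the last hour. A change score compared by ANOVA is valid under randomisation, so only an efficiency choice would remain. The size of that choice depends on quantities the documents do not give. Baseline and outcome come from one continuous infusion in one session, so a high correlation is plausible. At r = 0.8 and 0.7 SD, ANCOVA gains about 2 points over a change score, and at r = 0.9 about none. With k = 0.7 and r = 0.7 there is no gain.

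Much of this is fair. The merged reading is reasonable, and on it the gain ranges from nothing to substantial. The disagreement rates apply only while both readings stay open, and at high r they mostly restate the power gap (59% against 93% at r = 0.8 and 0.7 SD). But the text does not state the merged reading, and the abstract does not settle it. Even when merged, baseline is used only by subtraction.

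Two further objections change little. The plan's ANOVA covers three drug arms (3 × 19 = 57 error df), not four, but this moves power by less than 0.5 point. Making last-hour EGP the outcome may seem to demote the change endpoint. With baseline as covariate, however, ANCOVA on the last-hour value and on the change give the same treatment effect.

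**Conclusion.** The concern holds, and the plan should be changed. The primary outcome is not fixed to one definition, and no reading of the plan uses baseline EGP as a covariate. Under random allocation all three analyses have the same expected contrast, so this is not a correction of bias.

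The size is conditional on assumed correlations and SDs. At 0.7 SD with equal SDs, the power gain over a change score falls from 17 points at r = 0.3 (63% against 46%) to about none at r = 0.9. Over the raw last-hour analysis it rises from 4 points at r = 0.3 (63% against 59%) to 36 at r = 0.8 (95% against 59%). Apart from the small slope cost, ANCOVA is no less precise than either alternative at any correlation examined. Confidence in the size is moderate, because the documents supply none of the quantities it depends on.

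**What to change.** State one primary outcome, mean EGP over 240-300 minutes. Analyse it by ANCOVA across all four arms, with mean pre-dose EGP over -60 to 0 minutes as covariate and placebo as the fourth treatment level. Name dapagliflozin versus dapagliflozin/exenatide as the single primary contrast, and report the adjusted difference with its 95% confidence interval. Say to which remaining contrasts the Bonferroni correction applies. Show change from baseline to 240-300 minutes descriptively. State how subjects are allocated, since the interpretation depends on it.

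The cost is a revision of the analysis text, one error degree of freedom (76 to 75 in the four-arm model) and about 1.4% average variance inflation from estimating the slope. No samples, visits or subjects are added.
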